## 3. STUDY DESIGN

#### **3.1. Overall Study Design**

This is a Phase 1, randomized, double-blind, placebo-controlled, 2 fixed sequences, multiple dose study in healthy male and/or female recreational opioid users.

This study will consist of 3 phases: Screening and Qualification, Treatment phase, and Follow-up (see Figure 3-1).

After a Screening period of up to 27 days (Day -30 to Day -3), eligible subjects will be admitted to the clinical research unit (CRU) on Day -2. Subjects will be randomized to 1 of 2 fixed treatment sequences (28 subjects in Sequence 1, and 16 subjects in Sequence 2) on Day -1.

Subjects will be required to present a negative urine drug and alcohol screen upon admission on Day-2, except for tetrahydrocannabinol (THC). If THC is positive at admission, a cannabis intoxication evaluation will be done by an Investigator, and subjects may be permitted to continue in the study at the discretion of an Investigator. Subjects will then undergo a naloxone challenge where an initial 0.2 mg intravenous (IV) dose of naloxone hydrochloride (HCl) will be administered. The subject will be observed for signs or symptoms of opioid withdrawal. If there is no evidence of withdrawal within 1 minute (as assessed by a Clinical Opioid Withdrawal Scale [COWS] score of <5), an additional 0.6 mg IV dose of naloxone HCl will be given, and the subject will be observed for signs and symptoms of withdrawal for 5 minutes (as assessed by COWS). Subjects who present symptoms of withdrawal during the qualification process will be excluded from the study and will not be eligible to enter the Treatment phase.

In total, subjects will be confined to the CRU for approximately 20 days from Day -2 to Day 18 (until approximately 72 hours following the last study drug administration).

On Day 1, subjects will receive a single CCI IV dose of morphine. From Day 2 to Day 15, subjects will receive a CCI oral dose of AZD4041 or placebo once daily for 14 consecutive days. On the morning of Day 15, the CCI oral dose of AZD4041 or placebo will be combined with a single CCI IV dose of morphine.

In order to limit the number of subjects being treated with investigational product (IP) on any single day, eligible subjects should be assigned to different subgroups. Subgroup sizes should be limited to no more than 8 subjects. Dosing of subgroups should be staggered to occur on different days, with at least 2 days between the start of dosing for sequential subgroups.

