A Follow-up visit will occur approximately 7±2 days after the last study drug administration.

The schedule of activities of the study is described in Table 6-1.

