#### Table 6-1Schedule of Activities

	Screening	Qua	lification		Treatment Phase							Follow-up/End of Study/Early Termination 				
Day 	-30 to -3	-2	-1	1	2	3	4-6	7	8	9-13	14	15	16	17	18	22 (± 2)
Informed Consent 	Х															
Eligibility Criteria Review (Inclusion/Exclusion)	Х	х	Х	х												
Demographics	Х															
Height, Weight, and Body Mass Index	Х														x 	
Medical History	Х	x 														
Medical & Recreational Drug Uses History	Х	x6														
Study Restrictions Review		Х													Х	Х
Admission to CRU		Х														
Clinic Confinement		Х	х	Х	Х	х	Х	х	х	Х	х	Х	Х	Х	х	
Discharge from CRU 															Х	
Randomization			Х													

<sup>1 Individual end of study procedures may either be performed at the time of last confinement to the clinical site or at the last study visit.

<sup>2 All predose activities will be performed within a 60-minute window prior to treatment administration

<sup>3 The latest version of the consent form must be signed prior to a subject's inclusion (prior to any study-related procedures).

<sup>4 Weight only

<sup>5 Any changes since the last visit will be documented.

 Any changes since the last visit will be documented.

<sup>7 Discharge from the clinical site will occur approximately 72 hours after the last study drug administration.

	Screening	Qua	lification		Treatment Phase							Follow-up/End of Study/Early Termination 				
Day 	-30 to -3	-2	-1	1	2	3	4-6	7	8	9-13	14	15	16	17	18	22 (± 2)
Vital Signs 	Х	Х		Х	Х	Х	Х	Х	Х	Х	Х	Х	Х	Х	Х	Х
12-lead safety ECG 	Х	х		Х	Х	Х	Х	х	Х	Х	Х	х	х	Х	Х	Х
12-lead continuous digital ECG and ECG extractions 			X 	х	х	х	х	x	x	х	х	х	х	х	х	
ECG telemetry 			Х	Х	Х	Х	х	Х	Х	Х		X	х	х	Х	
Continuous SpO 2 , Respiratory Rate and EtCO 2 Monitoring 				x					x			x				
Spot SpO 2 	Х	х		Х	х	х	х	Х	X	х	Х	X	Х			Х
Spot Respiratory rate 	Х	Х		Х	Х	Х	Х	х	х	Х	Х	Х	Х			Х
Spot EtCO 2 				Х	Х	Х	Х	х	Х	Х	Х	Х	Х			

<sup>8 Vital sign measurements are detailed in Section 6.1.5.

<sup>9 12-lead safety ECG measurements are detailed in Section 6.1.6.1.

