# 8.1.3. Completer Population

The Completer Population will include all subjects in the Safety Population who complete the entire Treatment phase and the follow-up period (up to at least Day 22). This population will be used for inferential analysis of maximum postdose increase in EtCO2 ( $E_{max}$  (postdose – predose)), maximum postdose reduction in SpO2 ( $E_{max}$  (predose – postdose)), and maximum postdose decrease in respiratory rate ( $E_{max}$  (predose – postdose)).

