## 8.3.2. Safety Analysis

#### 8.3.2.1. Respiratory Depression Analysis

Summary statistics and inferential analysis for respiratory depression endpoints will be done using the Completer Population.

Incidence of increased EtCO2 of at least >50 mmHg will be summarized by treatment and time point using frequency tables. Mean time to each increased EtCO2 episode of at least >50 mmHg, mean duration of each increased EtCO2 episode of at least >50 mmHg, and mean postdose EtCO2 will be summarized by treatment and time point using descriptive statistics. Maximum postdose increase in EtCO2  $E_{max}$  (postdose – predose) will be summarized by treatment using descriptive statistics and inferential analysis. EtCO2 averages (predose average from Days 2 to 15), and postdose average on Day 15 will also be summarized by treatment using descriptive statistics and inferential analysis. For each event of significantly increased ETCO2, type of medical intervention used will be listed.

Incidence of reduction in SpO2 to <92% will be summarized by treatment and time point using frequency tables. Mean time to reduction in SpO2 to <92%, mean duration of reduction in SpO2 to <92%, and mean postdose SpO2 will be summarized by treatment and time point using descriptive statistics. Maximum postdose reduction of SpO2  $E_{max}$  (predose – postdose) will be summarized by treatment using descriptive statistics and inferential analysis. SpO2 averages (predose average from Days 2 to 15), and postdose average on Day 15 will also be summarized by treatment using descriptive statistics and inferential analysis. For each event of significantly reduced SpO2, type of medical intervention used will be listed.

Incidence of reduced respiratory rate to <6 breaths/min will be summarized by treatment and time point using frequency tables. Mean time to each reduced respiratory rate episode of < 6 breaths/min, mean duration of each reduced respiratory rate episode of <6 breaths/min, and mean postdose respiratory rate will be summarized by treatment and time point using descriptive statistics. Maximum postdose decrease in respiratory rate  $E_{max}$  (predose – postdose) will be summarized by treatment using descriptive statistics and inferential analysis. Respiratory rate averages

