4 ANALYSIS POPULATIONS

The following populations are defined for this study:

- **Randomized Population:** The randomized population will include all subjects who are randomized to the Treatment phase.
- **Safety population:** The safety population will include all subjects who received at least 1 dose of morphine, placebo, or AZD4041.
- **Completer Population:** The completer population will include all subjects in the safety population who completed the entire Treatment phase and the follow-up period (up to at least Day 22). This population will be used for inferential analysis of maximum postdose

increase in EtCO₂ (E_{max} (postdose – predose)), maximum postdose reduction in SpO₂ (E_{max} (predose – postdose)), and maximum postdose decrease in respiratory rate (E_{max} (predose – postdose)).

- **Pharmacokinetic Population:** All subjects in the safety population who received at least 1 dose of morphine or AZD4041 and have at least 1 PK concentration after dosing will be included in the PK population.

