9 SAFETY ANALYSIS

9.1 Respiratory Depression Analysis

Summary statistics and inferential analysis for respiratory depression endpoints will be presented for all subjects who completed all EtCO₂ assessments in addition to the Safety Population, when possible. Incidence of increased EtCO₂ of at least >50 mmHg will be summarized by treatment and time point using frequency tables. Mean time to each increased EtCO₂ episode of at least >50 mmHg, mean duration of each increased EtCO₂ episode of at least >50 mmHg, and mean postdose EtCO₂ will be summarized by treatment and time point using descriptive statistics.

Maximum postdose increase in EtCO₂ E_{max} (postdose – predose) will be summarized by treatment using descriptive statistics and inferential analysis. EtCO₂ averages (predose average from Days 2 to 15), and postdose average on Day 15 will also be summarized by treatment using descriptive statistics and inferential analysis. For each event of significantly increased ETCO₂, type of medical intervention used will be listed.

Incidence of reduction in SpO₂ to <92% will be summarized by treatment and time point using frequency tables. Mean time to reduction in SpO₂ to <92%, mean duration of reduction in SpO₂ to <92%, and mean postdose SpO₂ will be summarized by treatment and time point using descriptive statistics. Maximum postdose reduction of SpO₂ E_{max} (predose – postdose) will be summarized by treatment using descriptive statistics and inferential analysis. SpO₂ averages (predose average from Days 2 to 15), and postdose average on Day 15 will also be summarized by treatment using descriptive statistics and inferential analysis. For each event of significantly reduced SpO₂, type of medical intervention used will be listed.

Incidence of reduced respiratory rate to <6 breaths/min will be summarized by treatment and time point using frequency tables. Mean time to each reduced respiratory rate episode of < 6 breaths/min, mean duration of each reduced respiratory rate episode of <6 breaths/min, and mean postdose respiratory rate will be summarized by treatment and time point using descriptive statistics. Maximum postdose decrease in respiratory rate E_{max} (predose – postdose) will be summarized by treatment using descriptive statistics and inferential analysis. Respiratory rate averages (predose average from Days 2 to 15), and postdose average on Day 15 will also be summarized by treatment using descriptive statistics and inferential analysis.

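### The Completer Population's Day 22 minimum conflicts with the Day 22 ± 2 follow-up window, and SAP 4 and SAP 9.1 disagree on whether a compliant Day 20 or 21 subject stays in the Emax inference

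*SAP*

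**What the plan says.** **Definition.** SAP 4 defines completers as members of the safety population who "completed the entire Treatment phase and the follow-up period (up to at least Day 22". Protocol 8.1.3 words it almost identically: "complete the entire Treatment phase and the follow-up period (up to at least Day 22".

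**Use.** SAP 4 continues "This population will be used for inferential analysis of maximum postdose" change in EtCO2, SpO2 and respiratory rate, and Protocol 8.1.3 assigns the same three variables. Protocol 8.3.2.1 goes further: "Summary statistics and inferential analysis for respiratory depression endpoints will be done using the Completer Population".

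**Visit timing.** Protocol 3.1 states "A Follow-up visit will occur approximately 7±2 days after the last study drug administration". Table 6-1 and SAP Appendix A both head the follow-up column Day 22 with ± 2 days. Footnote 1 to Table 6-1 adds: "Individual end of study procedures may either be performed at the time of last confinement to the clinical site or at the last study visit".

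**A second analysis set.** SAP 9.1, which specifies the respiratory analysis, says that summaries and inference "will be presented for all subjects who completed all EtCO₂ assessments in addition to the Safety Population, when possible". It mentions neither the Completer Population nor Day 22.

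**The concern.** The population rule sets a minimum day equal to the nominal visit day, while the schedule permits the visit up to two days before it. SAP 5.1 gives an exact formula for Study Day, so a programmer could reasonably turn the rule into a flag of Study Day 22 or later. Two subjects with the same complete Day 1 and Day 15 respiratory data would then be classified differently because of the calendar date of an in-window visit. This needs no withdrawal, missing value or protocol deviation.

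The affected analysis matters: the Emax contrasts are the trial's main inferential comparison of morphine with and without AZD4041. Under Protocol 8.3.2.1 the same population also carries the descriptive respiratory summaries, including the primary incidence endpoints. In a trial of 44 randomised subjects, losing compliant subjects for an administrative reason costs precision. Leaving the choice of set open until the data are in hand leaves a discretionary decision that should have been made beforehand.

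**Working it through.** **1. Reproduce the planned visit day and window.** The last dose is on Day 15 (Protocol 3.1: "From Day 2 to Day 15, subjects will receive a CCI oral dose of AZD4041 or placebo once daily for 14 consecutive days").

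- Nominal visit: 15 + 7 = Day 22, as in Table 6-1.
- Window: 22 − 2 = Day 20 to 22 + 2 = Day 24.
- Cross-check: Day −30 to Day 24 with no Day 0 is 30 + 24 = 54 days, the maximum study duration given in the protocol synopsis. Day 24 is therefore the planned end of the window.

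**2. Apply the definition to each permitted day.**

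| Visit day | In window | Meets the Day 22 minimum |
|---|---|---|
| 20 | yes | no |
| 21 | yes | no |
| 22 | yes | yes |
| 23 | yes | yes |
| 24 | yes | yes |

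Two of the five permitted days fail.

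**3. Compare with the data the analysis uses.** The Emax contrasts in Protocol 8.3.2.1 and SAP 9.1 compare Day 1 and Day 15. The last scheduled reading in the Day 15 series for all three variables is at 24 hours, on Day 16 (Protocol Tables 6-8, 6-10 and 6-12). Spot SpO2 and respiratory rate are taken again at follow-up, by portable oximeter and counted breaths, but they do not enter the Day 1 and Day 15 contrasts. EtCO2 is not scheduled at follow-up. The follow-up date thus carries no information about Emax.

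**4. Trace a compliant Day 20 subject through each section.**

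| Section | Set named for Emax inference | Day 20 subject with complete EtCO2 data |
|---|---|---|
| SAP 4 | Completer Population | out, read literally |
| Protocol 8.1.3 and 8.3.2.1 | Completer Population | out, read literally |
| SAP 9.1 | All EtCO2 assessments completed | in |
| SAP 9.1 | Safety Population, when possible | in |

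No section says which takes precedence.

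**5. Size if the literal rule were applied.** Let q be the share of subjects seen on Day 20 or 21. The documents do not give q, so it is an assumption shown as a range. If q is the same in both sequences, each group size is multiplied by (1 − q), and the standard error of a mean or of a difference in means by 1/√(1 − q). This ignores the small effect on degrees of freedom. The counts start from all 28 and 16 randomised subjects finishing.

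| q | SE factor | Sequence 1, 28(1 − q) | Sequence 2, 16(1 − q) |
|---|---|---|---|
| 0% | 1/√1.0 = 1.00 | 28 | 16 |
| 10% | 1/√0.9 = 1.05 | 25.2 | 14.4 |
| 20% | 1/√0.8 = 1.12 | 22.4 | 12.8 |
| 40% | 1/√0.6 = 1.29 | 16.8 | 9.6 |

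The 40% row is what an even spread over the five permitted days would give (2/5). It illustrates the upper part of the range and is not a forecast.

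**The case against.** **SAP 9.1 would keep the subject.** This is the strongest point, and it stands. A reader might infer from SAP 4 alone that a compliant Day 20 or 21 subject is dropped from the Emax inference. SAP 9.1 describes that same inference on sets with no Day 22 condition. But it does not withdraw the assignment in SAP 4, and Protocol 8.1.3 and 8.3.2.1 side with SAP 4. The result is two answers for one analysis, so the exclusion is possible but not established.

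**The parenthesis may only label the visit.** The operative requirement is to complete the follow-up period, and Table 6-1 calls the whole Day 20 to 24 visit Day 22. That may be what was meant. Neither document says so, however, and wording that sets a minimum invites the strict reading.

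**The planned numbers are not breached.** A reader might infer that the target of 24 + 12 completers could be missed. Protocol 8.5 and the synopsis tie that target to Day 15, so a later visit date cannot affect it. With no formal sample size calculation, no planned power is breached either.

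**The loss may be nil.** Also true. The visit is aimed at about 7 days after the last dose, which is Day 22, and if no visit is early nobody is lost. A reader might take the 40% case as the expected loss, but nothing in the documents supports an even spread.

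**Footnote 1 does not add to the count.** It lets individual procedures be done at last confinement, with discharge on Day 18, but it does not waive the follow-up visit. At most it blurs what completing follow-up means.

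**Conclusion.** The mismatch is real and appears in both documents: a Day 22 minimum in the population definition against a visit window that opens on Day 20. Under SAP 4 and Protocol 8.1.3 and 8.3.2.1, read literally, 2 of the 5 permitted visit days exclude a compliant subject for a reason unrelated to the Emax data.

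Whether anyone would be excluded is not settled, because SAP 9.1 names other sets for the same inference. The cost under the literal rule ranges from nothing to standard errors about 5%, 12% or 29% larger at 10%, 20% or 40% early visits. Those figures assume an equal early share in both sequences, which the documents neither give nor rule out. The case shown is one of lost precision and an open choice of analysis set; the documents give no ground to claim bias.

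The point should be corrected before database lock. SAP 5.1 treats analyses performed after lock or unblinding as post hoc, so a choice of set made then would be hard to defend as prespecified.

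**What to change.** Preferred: define the set for the Emax inference by evaluable Day 1 and Day 15 respiratory data, with no condition on the follow-up visit.

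Minimum: keep the Completer Population but replace its Day 22 parenthesis with a requirement that the follow-up visit was performed within its window (Day 22 ± 2). All five permitted days then qualify.

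In either case, name that one set as the basis for the Emax inference in SAP 4, SAP 9.1 and Protocol 8.1.3 and 8.3.2.1. If results on the Safety Population are wanted as well, say that they are supportive.

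The cost is a phrase in the definition and a matching sentence in the other sections. It needs no new data, visits or assessments.

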5 DATA HANDLING AND PRESENTATION

5.1 Safety Analysis Presentation

Adverse events and medical history will be classified using the Medical Dictionary for Regulatory Activities (MedDRA) terminology as defined in the study Data Management Plan (DMP).

Prior and concomitant medications will be coded with the World Health Organization Drug Dictionary (WHODrug) as defined in the study DMP.

In general, all safety summary tables will be presented for the safety population. Summaries for AEs will be presented by treatment and treatment sequence. Summaries for other safety endpoints will be presented by treatment if the endpoints are measured at the end of each period or by treatment sequence if the endpoints are not measured at the end of each period (End of Study only).

In general, the data listings will include all subjects in the safety population up to the point of study completion or discontinuation; exceptions will be listings pertaining to a subset of subjects only (eg, subjects with protocol deviations) or a subset of records/events (eg, abnormal laboratory values). Limited data for those not included in the safety population, eg, who failed screening, may be presented, as appropriate.

Categorical variables will be summarized using sample size (N), number of available data (n), and the percentage of available data (%) for each class. Continuous variables will be summarized using descriptive statistics, including N, n, arithmetic mean (mean), standard deviation (SD), minimum (min), median, and maximum (max).

The following general considerations may be applied:

- Study Day will be derived from the reference date (eg, the day of the first dose of study drug) and date of event as:
Study Day = (date of event – reference date) +1, if event is on or after the reference date;
Study Day = date of event – reference date, if event is before the reference date.
- Duration will be calculated using the general formula: (end date - start date) +1.
- If the reported value of a clinical laboratory parameter cannot be used in a statistical summary table (eg, a character string is reported for a parameter of the numerical type), a coded value may be appropriately determined and used in the statistical analyses. In general, a value below the lower limit of normal range such as ‘<10’ or ‘≤5’ will be treated as half of the lower limit, ‘5’ or ‘2.5’, respectively, and a value above the upper limit of normal range such as ‘>100’ will be replaced with a number deemed scientifically reasonable, eg, 101. However, the actual values as reported in the database will be presented in data listings.

- Unscheduled assessments will not be included in descriptive summary, except for baseline consideration. When assessments are repeated for a given timepoint or performed at unscheduled times, only the result which is the closest to the assessment time will be included in summary tables.

In general, summary statistics for raw variables (ie, variables measured at the study site or central laboratory) will be displayed as follows:

- Minima and maxima will be displayed to the same number of decimal places as the raw data
- Means, medians, and quartiles (if presented) will be displayed to 1 additional decimal place
- Standard deviations will be displayed to 2 additional decimal places
- Percentages will be displayed to 1 decimal place; Percentages between 0 and 0.1 (exclusive) will be displayed as '<0.1'
- P-values will be displayed to 3 decimal places; p-values that are less than .001 will be displayed as '<.001'

Derived variables (ie variables that are not measured by the study site but are calculated for analysis based on other measured variables) will be displayed with the same precision as the raw data, as appropriate, then will follow similar rules in presentation of summary statistics.

All outputs will be generated using SAS software version 9.4 or higher.

The analyses described in this plan are considered a priori, in that they have been defined prior to database lock and/or prior to breaking the blind. Any analyses performed subsequent to database lock and/or breaking the blind will be considered post hoc and exploratory, and will be identified in the Clinical Study Report (CSR).

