## 7.4. Adverse Event Monitoring

For the purposes of this study, the monitoring period for AEs extends from the pre-trial evaluation until the follow-up visit. Registration of new AEs will start from the moment of ICF signature and will stop 7 days after the last study drug administration (ie, stop registration on new AEs on follow-up visit in case last AZD4041 dose was administered on Day 15).

Subjects will be questioned on their health status from the beginning of the study, before departure from the clinical site, and at the follow-up visit. Open-ended questions will be asked.

During the study, all AEs reported by the subject, observed by the clinical staff, or elicited by general questioning will be recorded for all subjects and reported in the CRF.

From the signing of the ICF until the first study drug administration, AEs will be recorded as screening events or as part of on the medical history eCRF page, as applicable. AEs occurring after study drug administration will be recorded on AE eCRF page and indicated as TEAEs in the Clinical Study Report, as well as non-serious AESI (defined in Section 7.1).

Any AE which remains unresolved as of the last study visit will require an evaluation and follow-up until the AE has been resolved, stabilized or a reasonable explanation for its persistence found, or is deemed mild and safely resolving.

In the case of AEs deemed related to the IP, every effort will be made to determine the final outcome.

If necessary, every effort will be made to obtain an adequate follow-up of the subjects. Should any subject choose to withdraw from the study, they will be advised of the safety precautions to be taken. For those subjects whose status is unclear because they fail to appear for study visits

without stating an intention to withdraw, Investigator should show "due diligence" by documenting in the source records steps taken to contact the subject, (eg, dates of at least three telephone call attempts, registered letters, etc).

It is an Investigator's responsibility to ensure subjects experiencing AEs receive appropriate follow-up, treatment where required, and that every action is well documented.

Classification of AEs will be performed by System Organ Class (SOC) and Preferred Term (PT) using the Medical Dictionary for Regulatory Activities (MedDRA), version 24.1 or higher.

Concomitant medications will be coded using the World Health Organization Drug Dictionary Enhanced (WHO-DDE March 2021 or later).

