3.4 Randomization and Unblinding Procedures

Subjects will be randomized into treatments as Sequence 1 or Sequence 2, as described in section 3.2. Sequence 1 will include 28 subjects total and Sequence 2 will include 16 subjects total. The total 44 subjects will be assigned into 6 Blocks, with Block 1 including 4 subjects (Sequence 1 to Sequence 2, 1:1), Blocks 2 through 5 including 8 subjects each (Sequence 1 to Sequence 2, 5:3), and Block 6 includes 8 subjects (Sequence 1 to Sequence 2, 3:1). Replacements may be made if subjects drop out of the study before completion.

The randomization code must not be broken except in emergency situations where the identification of a subject's study treatment is required by an Investigator for further treatment to the subject or to complete a SAE report. Randomization information will be held by designated individual(s). The date and reason for breaking the blind must be recorded.

Unblinding of the data will occur after database lock except in cases of emergency.

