9.8 All Other Safety Analysis

Summary statistics for all other safety analysis will be done using the Safety Population.

All AEs will be coded using the Medical Dictionary for Regulatory Activities (MedDRA) and characterized as pre-treatment and treatment-emergent according to the intake of the study drugs. The occurrence and incidence of TEAEs will be summarized by MedDRA system organ class and preferred term and by treatment. The occurrence and incidence of TEAEs will also be

summarized by severity and by relationship to the study drugs. Adverse events leading to discontinuation and SAEs will be listed.

Values within and outside the reference range will also be summarized using frequency tables. Physical examination abnormalities and C-SSRS findings will be listed.

Unless otherwise specified, all available data will be listed and summary tables for safety assessments will be presented for the safety population.

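### TEAE incidence by treatment compares columns with about 1, 13 and 7 days at risk, so the Day 15 and Day 1 columns are not comparable; the randomized Day 15 comparison is not affected

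*SAP*

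**What the plan says.** SAP 5.1 gives the general rule for adverse events: "Summaries for AEs will be presented by treatment and treatment sequence". SAP 9.8, which repeats Protocol 8.3.2.3, adds that "The occurrence and incidence of TEAEs will be summarized by MedDRA system organ class and preferred term and by treatment", with further summaries by severity and relationship. Events are "characterized as pre-treatment and treatment-emergent according to the intake of the study drugs". Neither document says which treatment column a treatment-emergent event belongs to or when one treatment's window ends and the next begins. No window of equal length and no rate per subject-day is planned.

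The treatment order is fixed for everyone. Protocol 3.1: "On Day 1, subjects will receive a single CCI IV dose of morphine". Then: "From Day 2 to Day 15, subjects will receive a CCI oral dose of AZD4041 or placebo once daily for 14 consecutive days". The last of these oral doses is given on Day 15 together with the second morphine infusion. Under Protocol 7.4, registration of new adverse events "will stop 7 days after the last study drug administration". The visit that closes it has a tolerance: "A Follow-up visit will occur approximately 7±2 days after the last study drug administration".

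Both sequences follow the same calendar. On allocation, SAP 3.4 says: "Sequence 1 will include 28 subjects total and Sequence 2 will include 16 subjects total".

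**The concern.** Protocol Section 2 makes safety and tolerability of AZD4041 given with morphine a secondary objective, with AE incidence among its endpoints. The primary objective compares morphine after AZD4041 with morphine alone. A reader of a by-treatment TEAE table will therefore set the Morphine + AZD4041 column beside the morphine-alone column.

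If those columns cover about 7 days and about 1 day, a crude percentage mixes any drug effect with time at risk. Two errors are possible. Ordinary background events (a headache on Day 19, for instance) can make the combination look less well tolerated than morphine alone. Conversely, a real acute difference can be diluted by several days of unrelated events.

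SAP 5.1 classes any analysis made after database lock or unblinding as post hoc and exploratory, so the window should be fixed beforehand.

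**Working it through.** **Inputs from the documents**
- Morphine alone: Day 1 infusion to Day 2 oral dose, 2 − 1 = about 1 day (Protocol 3.1).
- AZD4041 or placebo alone: Day 2 dose to Day 15 dose, 15 − 2 = 13 days. The dose count 15 − 2 + 1 = 14 agrees with the protocol's 14 consecutive days.
- Combination: Day 15 to Day 22, 22 − 15 = 7 days, which reproduces the 7 days in Protocol 7.4. With the ±2-day visit tolerance the visit falls 5 to 9 days after the last dose.
- Scheduled total in either sequence: 1 + 13 + 7 = 21 days.

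**Assumptions not in the documents**
- Each event is assigned to the most recent treatment.
- The background probability r of a new event per subject-day is constant and unrelated to treatment; r = 1%, 2% and 5% are used.

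**Step 1. No drug effect and no acute morphine events.** Incidence over d days is 1 − (1 − r)^d.

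| r per day | 1 day (morphine alone) | 7 days (combination) | 13 days (oral drug alone) | 7 vs 1 | 7 vs 13 |
|---|---|---|---|---|---|
| 1% | 1.0% | 6.8% | 12.2% | 6.8 | 0.55 |
| 2% | 2.0% | 13.2% | 23.1% | 6.6 | 0.57 |
| 5% | 5.0% | 30.2% | 48.7% | 6.0 | 0.62 |

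At 2% per day, 28 subjects give 28 × 0.020 = 0.6 expected subjects with an event in the morphine-alone column and 28 × 0.132 = 3.7 in the combination column.

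**Step 2. Sensitivity.** At 5 days the ratio to Day 1 is 4.9 to 4.5 (r = 1% to 5%); at 9 days it is 8.6 to 7.4. In the continuous form, 1 − exp(−rate × t), the 7-day ratio is 6.9 at 0.005 per day and falls to 4.2 at 0.20 per day.

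**Step 3. Add acute morphine events.** Let a fraction a of subjects have an acute event after each infusion, equally on both days (assumed a = 30% or 60%). Any-event incidence is 1 − (1 − a)(1 − r)^d.

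| a | r per day | Day 1 (d = 1) | Day 15 (d = 7) | Ratio |
|---|---|---|---|---|
| 30% | 1% | 30.7% | 34.8% | 1.13 |
| 30% | 2% | 31.4% | 39.2% | 1.25 |
| 30% | 5% | 33.5% | 51.1% | 1.53 |
| 60% | 1% | 60.4% | 62.7% | 1.04 |
| 60% | 2% | 60.8% | 65.3% | 1.07 |
| 60% | 5% | 62.0% | 72.1% | 1.16 |

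These are any-event figures. A preferred term that morphine does not cause acutely still follows Step 1, so its row stays inflated by the Step 1 ratio.

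**Step 4. Randomized comparisons.** Morphine + AZD4041 and Morphine + Placebo on Day 15 both have d = 7, and the two sequences both have 21 days. The ratio from window length alone is 1.0 in each case.

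**Step 5. With an equal window.** Restricting both morphine days to the same 24 hours puts d = 1 on each side. At r = 5% and no acute events, incidence is 5.0% on both days and the ratio is 1.0.

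**The case against.** A fair comparison is already in the plan. The SAP 5.1 sentence also promises summaries by treatment sequence, where both arms have the same scheduled observation, and the two Day 15 columns have equal windows. For tolerability of AZD4041 with morphine, the randomized Day 15 contrast is the right one. Sequence 2 also shows how Day 15 differs from Day 1 without AZD4041. This stands, and it limits the point to the within-subject reading. The SAP does not, however, name the randomized contrast as the main AE comparison, and its existence does not repair the Day 15 versus Day 1 columns.

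The treatment columns are themselves an inference. For the digital ECG (SAP 9.2), treatment means two arms, and the table layouts are in a separate document (SAP 12). This also stands. The missing assignment rule is therefore the firmer half of the point, and the 1/13/7-day split is conditional on it.

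A ratio of 6 or 7 assumes no acute morphine events, although Protocol 1.3.2.1 calls the morphine dose supratherapeutic. Step 3 shows how far the any-event ratio falls once they are allowed for.

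The stakes are bounded. The AE tables are descriptive, and no test or sample size depends on them. Respiratory depression is measured separately on closely matched Day 1 and Day 15 schedules, with its own contrasts (Protocol 6.1.8 to 6.1.10; SAP 9.1). Other acute adverse events have no such cover.

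Finally, the documents do not expressly say that AE onset clock time is captured. SAP 5.1 derives study day and duration from dates, so the fix must also work with dates.

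**Conclusion.** The point holds in a limited form. If events are assigned to the most recent treatment, the by-treatment TEAE table sets about 1 day at risk beside about 7 and 13 days, and the Day 15 and Day 1 percentages cannot be compared directly. From window length alone the ratio is about 6 to 7 under a constant 1% to 5% daily background with no acute morphine events. For any event it is about 1.1 to 1.5 at 2% to 5% background when 30% to 60% of subjects have an acute event on both days, and lower still at 1% background (1.04 to 1.13). The daily rates and acute fractions are assumptions. The day counts come from the schedule.

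A reader might infer three stronger things that the documents do not support:
- **That the combination looks worse in general.** Against the 13-day column it looks better (ratio 0.55 to 0.62), and against Morphine + Placebo on Day 15 there is no window effect.
- **That overall AE incidence will be inflated six- or seven-fold.** That requires morphine to cause no acute events.
- **That follow-up after the combination lasts 7 days or longer.** The visit falls 5 to 9 days after the last dose, and Protocol 7.4 sets the end of new-event registration at 7.

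This is an inexpensive improvement to a descriptive table. It does not threaten the trial's inference.

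**What to change.** In SAP 9.8, before database lock:

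1. State the rule that assigns each TEAE to a treatment, including when each treatment's window opens and closes.
2. Add one TEAE table with an equal post-morphine window on Day 1 and Day 15: for example, onset within 24 hours of the end of infusion and, on Day 1, before the Day 2 oral dose. If AE clock times are not captured, use onset on the infusion date. Show Day 15 versus Day 1 within each sequence, and AZD4041 versus placebo on Day 15.
3. Name Morphine + AZD4041 versus Morphine + Placebo on Day 15 as the main AE comparison.
4. Compare AZD4041 alone with placebo only between sequences, over Days 2 to 14.
5. Keep the existing all-onset table, with subject-days at risk in the column headers. If everyone completes with 7 days of follow-up, Sequence 1 would show 28 × 1 = 28, 28 × 13 = 364 and 28 × 7 = 196; Sequence 2 would show 16, 208 and 112.

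The cost is one additional descriptive table, with fewer events per cell. The 24-hour cut-off is an example; the documents do not single out any length, and what matters is that both days use the same one. An equal window removes the time-at-risk difference but not any order effect between Day 1 and Day 15, which is why the randomized contrast should lead. Dosing, visits and sample size do not change.
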